### **8.2.3           Intensity**

The intensity of an AE will be graded according to [Guidance for Industry: Toxicity Grading Scale for Healthy Adult and Adolescent Volunteers Enrolled in Preventive Vaccine Clinical Trials \(September 2007\)](#). The grading scale is comprised of 4 levels: mild (Grade 1), moderate (Grade 2), severe (Grade 3), and potentially life-threatening (Grade 4). For those AEs that are not covered in the Guidance for Industry (above) the rating scale from [DAIDS \(Table for Grading the Severity of Adult and Pediatric Adverse Events, Version 2.1\)](#) will be used (Table 8-1).

**Table 8-1       DAIDS Adverse Events Intensity Assessment**

Grade	Intensity	Definition
Grade 1	Mild	Symptoms causing no or minimal interference with usual social and functional activities with intervention not indicated.
Grade 2	Moderate	Symptoms causing greater than minimal interference with usual social and functional activities with intervention indicated.
Grade 3	Severe	Symptoms causing inability to perform usual social and functional activities with intervention or hospitalization indicated.
Grade 4	Potentially Life-Threatening	Symptoms causing inability to perform basic self-care functions with intervention indicated to prevent permanent impairment, persistent disability, or death.
Grade 5		Any AE where the outcome is death

### **8.2.4       Relationship to Study Vaccine**

The relationship of an AE to the study vaccine should be determined by the Investigator according to the following criteria:

- Not related: The event is most likely produced by other factors such as the subject's clinical condition, intercurrent illness, or concomitant drugs, and does not follow a known response pattern to the study vaccine, or the temporal relationship of the event to study vaccine administration makes a causal relationship unlikely

- Related: The event follows a reasonable temporal sequence from the time of drug administration, and/or follows a known response pattern to the study vaccine, and cannot be reasonably explained by other factors such as the subject's clinical condition, intercurrent illness, or concomitant drugs

### **8.3 Discontinuation Due to Adverse Events**

Any subject who experiences an AE may be withdrawn at any time from the study at the discretion of the Investigator. Subjects withdrawn from the study due to an AE, whether serious or nonserious, may be followed by the Investigator until the clinical outcome of the AE is determined. The subject will also be asked to participate in a Follow-up Visit at approximately Day 365 to check safety and immunogenicity. The AE(s) should be noted on the appropriate eCRFs, the subject's progress should be followed until the AE is resolved or medically stable as determined by the Investigator, and the Sponsor notified.

### **8.4 Reporting Serious Adverse Events and Adverse Events of Special Interest**

In the event of any SAE or AESI reported or observed during the study, whether or not attributable to the study vaccine, site personnel will report it immediately by telephone to the Sponsor, medical monitor, AND SAE hotline at ICON (ICON Pharmacovigilance) in accordance with procedures described in the SRM and/or SAE SSP. Site personnel will follow up with a written report on the next working day.

Report Forms will be provided to the CRU to assist in collecting, organizing, and reporting SAEs or AESIs and follow-up information.

All SAEs and AESIs should be followed to their resolution, with documentation provided to the Sponsor/ICON on a follow-up Report Form.

### **8.5 Pregnancy**

Pregnancies will be captured if they occur in female subjects from the time the subject is first exposed to the study vaccine until EOS. Pregnancies in the sexual partners of male subjects will be captured from the time the subject is first exposed to the study vaccine until 90 days after last exposure to the study vaccine.

Female subjects must be instructed to inform the study Investigator immediately if they become pregnant during the study.

The Investigator must report any pregnancy to the medical monitor, Sponsor, and ICON Pharmacovigilance within 1 business day of becoming aware of the pregnancy per pregnancy reporting procedures described in the SRM. The subject must be immediately discontinued from further treatment with study vaccine. An uncomplicated pregnancy will not be considered an AE or SAE; however, all pregnancies will be followed through birth and 3 months postdelivery.

Any congenital abnormalities in the offspring of a subject who received study vaccine will be reported as an SAE. The outcome of any pregnancy and the presence or absence of any congenital

abnormality will be recorded in the source documentation and reported to the Sponsor and ICON Pharmacovigilance.

## **8.6 Drug-induced Liver Injury**

Subjects will be monitored for signs of DILI. Study vaccine (dose 2) will be withheld in the event of potential DILI.

Potential events of DILI will be defined as meeting all of the following criteria (as specified in the [FDA Guidance for Industry Drug-induced Liver Injury: Premarketing Clinical Evaluation, 2009](#)):

- ALT or AST  $>3 \times$  ULN
- Total bilirubin  $>2 \times$  ULN without initial findings of cholestasis (elevated serum ALP)
- No other reason can be found to explain the combination of laboratory value increases (eg, acute viral hepatitis; alcoholic and autoimmune hepatitis; hepatobiliary disorders; nonalcoholic steatohepatitis; cardiovascular causes; concomitant treatments)

Potential events of DILI will be reported as SAEs ([Section 8.4](#)). All subjects with potential DILI will be closely followed until abnormalities return to normal or baseline or until reasonable attempts to determine resolution of the event are exhausted.

## **9 STATISTICAL CONSIDERATIONS**

The statistical analysis will be conducted following the principles as specified in ICH Topic E9 (CPMP/ICH/363/96).

All statistical analyses will be described in a separate SAP.

The statistical evaluation will be performed using SAS® software version 9.4 or higher (SAS Institute, Cary, NC). All data will be listed, and summary tables will be provided. No formal significance testing will be performed. Summary statistics will be presented by treatment group and include subset analysis (eg, all subjects, seronegative subjects [ie, neutralizing antibody titer < 10 at screening], seropositive subjects, and subjects that received an FDA Emergency Use Authorization/licensed COVID vaccine). For continuous variables, data will be summarized with the number of subjects, mean, standard deviation, median, minimum, maximum, geometric mean, CV%, GeoCV%, and 95% CI by treatment group. For categorical variables, data will be tabulated with the number and proportion of subjects for each category by treatment group.

The database will be locked and unblinded after the data have been monitored for all subjects through Day 43. Details of the unblinded interim analysis are presented in [Section 9.5](#).

The final analysis of the safety and immunogenicity data collected from Day 43 through Day 365/approximately 1 year after first vaccination will be performed after the study is completed. An addendum to the initial CSR will be prepared with data from final analysis. Details of the statistical analyses, methods, and data conventions will be described in the SAP.

### **9.1 Sample Size Calculation**

No formal sample size calculation was performed.

A total of 180 subjects will be enrolled in Parts A and B. Approximately 90 eligible subjects (aged 18-49 years), with 30 subjects per treatment group for Part A and 90 eligible subjects (aged 50-85 years), with 30 subjects per treatment group for Part B, will be enrolled in the study.

An optional Part C Expansion may be conducted to confirm the safety and immunogenicity of the selected dose of vaccine in up to 1000 adult subjects randomized 1:1 (single dose level of study vaccine:placebo). The proposed sample size was selected based on [WHO guidelines on clinical evaluation of vaccines: regulatory expectations Annex I \(2001\)](#), which states that approximately 300 subjects are needed to identify common local reactogenicity events. A larger sample size will assist in a better characterization of kinetics and range of immunity (neutralizing antibody titers) and provide a more reliable output of seropositivity and seroconversion to TAP-COVID-19 immunization. With the limited clinical experience with SARS-CoV-2 vaccines and the current lack of a biomarker correlate of protection, the generation of this larger data set is relevant to inform the design and implementation of a Phase 3 program.

### **9.2 Analysis Populations**

Enrolled Population: All subjects who signed the ICF.

**Safety Population:** All subjects who provide consent, are randomized, and receive any amount of study vaccine/placebo. The Safety Population will be used for the demographic, baseline characteristic, safety data summaries, and the analysis of primary endpoints such as occurrence of solicited local and systemic reactogenicity.

**Per Protocol (PP) Population:** Includes all subjects in the Safety Population who receive the assigned doses of the study vaccine/placebo according to protocol, have serology results, and have no major protocol deviations affecting the primary immunogenicity outcomes, as determined by the Sponsor before database lock and unblinding. Subjects that are immunized with an approved vaccine will be captured as a subset analysis of the PP Population at Days 90, 181, 273, and 365 based on the date of receiving an approved COVID-19 vaccine.

**Modified Intent-to-Treat (mITT) Population:** Includes all subjects in the Safety Population who provide any serology data. The mITT Population will be used for the immunogenicity analysis.

### **9.3 Randomization**

The overall randomization for the study will be 2:1 (active:placebo). Each Part (A and B) and treatment (low and high) will be randomized individually 2:1 (active to placebo).

The study will start with Part A (18-49 years) low dose, randomized in a 2:1 ratio (30 subjects active:15 subjects placebo) for Treatment A (15 µg TAP-COVID-19 vaccine + 0.5 mg CpG).

Part A (18-49 years) high dose will be randomized in a 2:1 ratio (30 subjects active:15 subjects placebo) for Treatment B (45 µg TAP-COVID-19 vaccine + 0.5 mg CpG) after Part A low dose has completed enrollment and the iSRC has reviewed safety and tolerability data through Day 8.

Part B (50-85 years) low dose will be randomized in a 2:1 ratio (30 subjects active:15 subjects placebo) for Treatment A (15 µg TAP-COVID-19 vaccine + 0.5 mg CpG) after Part A low dose has completed enrollment and received the first vaccination and the iSRC has reviewed safety data through Day 8.

Part B (50-85 years) high dose will be randomized in a 2:1 ratio (30 subjects active:15 subjects placebo) for Treatment B (45 µg TAP-COVID-19 vaccine + 0.5 mg CpG) after Part B low dose has completed enrollment and received the first vaccination and the iSRC has reviewed safety data through Day 8.

A total of 90 subjects will be randomized in Part A (18-49 years); 30 subjects low dose (Treatment A, 15 µg TAP-COVID-19 vaccine + 0.5 mg CpG), 30 subjects high dose (Treatment B, 45 µg TAP-COVID-19 vaccine + 0.5 mg CpG), and 30 subjects placebo (Treatment C).

A total of 90 subjects will be randomized in Part B (50-85 years); 30 subjects low dose (Treatment A, 15 µg TAP-COVID-19 vaccine + 0.5 mg CpG), 30 subjects high dose (Treatment B, 45 µg TAP-COVID-19 vaccine + 0.5 mg CpG), and 30 subjects placebo (Treatment C).

Treatment A: TAP-COVID-19 vaccine (15 µg) + CpG (0.5 mg) IM injection on Day 1 and Day 22 ( $\pm 3$  days)

CONFIDENTIAL

Treatment B: TAP-COVID-19 vaccine (45 µg) + CpG (0.5 mg) IM injection on Day 1 and Day 22 ( $\pm 3$  days)

Treatment C: Placebo (buffered saline solution) IM injection on Day 1 and Day 22 ( $\pm 3$  days)

A computer-generated randomization schedule for each part (Part A, Part B, and Part C Expansion) will be generated prior to study start by an ICON biostatistician.

For sentinel dosing, 3 subjects from each part will be randomized 2:1 (active:placebo). The remainder of each cohort will also be randomized 2:1 (active:placebo).

#### **9.4 Endpoints**

Endpoints are presented in [Section 3.2](#).

#### **9.5 Interim Analyses**

An unblinded interim analysis will be performed on the safety and immunogenicity data collected for each of the 4 dose groups (Part A low dose, Part A high dose, Part B low dose, and Part B high dose). Unblinded interim analysis will occur for the Part A low dose group (including active and placebo subjects) when the first 30 subjects vaccinated have data available from Day 1 through Day 43. The remaining cohorts will have an unblinded interim analysis performed when all subjects in the cohort have data from Day 1 through Day 43. For the interim analysis, treatment codes will be unblinded after the data are deemed ready for the analysis and the data has been monitored. The CRO [except for the unblinded team members preparing the data for unblinded iSRC review], Investigator, and clinical staff will not have access to the unblinded treatment group interim analyses and will remain blinded until completion of the study. The Sponsor will be unblinded at the interim analysis. Safety and immunogenicity analyses from this unblinded interim analysis will be presented in a CSR. This CSR may be submitted to regulatory authorities as needed.

#### **9.6 Immunogenicity Analysis**

The mITT Population will be used for all listings and summary statistics corresponding to immunogenicity analysis.

The individual sampling and blood collection for ELISA analysis to determine IgG and IgM antibody titers to the spike RBD and neutralizing antibody titers for parent (Wuhan) and any variant SARS-CoV-2 strains, will be listed and summarized by time points for each part by treatment.

All derived immunogenicity secondary endpoint parameters: GMT, GMT ratio, GMFR, GMI, and seroconversion rates will be listed and summarized by scheduled time point using descriptive statistics (n, mean, SD, minimum, median, maximum, geometric mean, CV%, GeoCV%, and 95% CI) for each part by treatment.

PBMC and serum sample data for future research results at each scheduled visit will also be provided separately in a listing and summary table, if applicable.

Subgroup analysis for safety and efficacy will be performed for those subjects who were seropositive when enrolled.

Graphical display of the summary results or at individual time points will be provided as needed (eg, scatter plots of subject titer values to visually display individual data points).

Additional details for analysis of immunogenicity are presented in the SAP.

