Both Part A (18-49 years) and Part B (50-85 years) will be randomized in a 2:1 ratio (active:placebo) for each treatment dose (15 µg and 45 µg TAP-COVID-19 vaccine + 0.5 mg CpG) for a total of 90 subjects per Part (30 subjects 15 µg TAP-COVID-19 vaccine + 0.5 mg CpG:30 subjects 45 µg TAP-COVID-19 vaccine + 0.5 mg CpG:30 subjects placebo).

Treatment A: TAP-COVID-19 vaccine (15 µg) + CpG (0.5 mg) IM injection on  
Day 1 and Day 22 ( $\pm 3$  days)

CONFIDENTIAL

Treatment B: TAP-COVID-19 vaccine (45 µg) + CpG (0.5 mg) IM injection on Day 1 and Day 22 ( $\pm 3$  days)

Treatment C: Placebo (buffered saline solution) IM injection on Day 1 and Day 22 ( $\pm 3$  days)

Study vaccine will be prepared by an unblinded site pharmacist and administered at the clinical research site on Day 1 and Day 22 ( $\pm 3$  days) by unblinded CRU personnel. Subjects will be observed for immediate AEs and/or reactogenicity for approximately 60 minutes after administration of vaccine. Subjects will be provided with a Diary Card and will be trained to record specifically elicited systemic and local symptoms daily as well as any additional AEs during the 7-day follow-up period after each vaccination. Visits will be conducted at the clinical site on an outpatient basis or as a telephone visit per the Schedule of Assessments and Procedures ([Table 1-1](#)). Subjects will participate in the study for approximately 1 year from the first dose.

AEs and concomitant medications will be captured through Day 43. Blood and serum samples for safety laboratory tests, RBD IgG and IgM antibodies, and neutralizing antibody titers, cell-mediated immunity, and other future biomedical research will be obtained at baseline and before administration of vaccine dose 2 and after each vaccination per the Schedule of Assessments and Procedures ([Table 1-1](#)). SAEs, MAAEs, NOCDs, and AESIs only will be captured after Day 43 to study completion (Day 365 [approximately 1 year after vaccination]).

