23. Individuals who plan to receive another vaccine within the first 3 months of the study except influenza vaccine which should not be given within 2 weeks of study vaccine.
24. Receipt of any other approved SARS-CoV-2 vaccine prior to the first study vaccine or within 90 days after administration of the first study vaccine.
25. Receipt of any other experimental coronavirus vaccine at any time prior to or during the study.
26. Receipt of any investigational vaccine or drug within 1 month of enrollment and through the end of the study (1 year after first vaccination).

27. Plan to travel outside the subjects' country of residence from enrollment through Day 43.
28. History of surgery or major trauma within 12 weeks of screening, or surgery planned during the study.
29. Significant blood loss (>450 mL) or has donated 1 or more units of blood or plasma within 6 weeks prior to study participation.
30. Strenuous activity (as assessed by the Investigator) within 48 hours prior to dosing (Days 1 and 22).
31. A positive urine drug screen without evidence of corresponding prescribed concomitant medication(s) at Screening. Note: A positive drug screen result with a corresponding prescribed concomitant medication will be allowed if, in the opinion of the investigator and Medical Monitor, the concomitant medication does not make the subject unsuitable to participate in the clinical trial. For a positive tetrahydrocannabinol result, refer to Exclusion Criteria #17.
32. Positive alcohol screen.
33. Positive screen for HIV-1 and HIV-2 antibodies, HBsAg, or HCV antibody.
34. Involved in the planning or conduct of this study.
35. Unwilling or unlikely to comply with the requirements of the study.
36. Subject is an employee, contractor, friend of or relative of any employee of Sponsor, CRO, study site or site affiliate.

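### Late immunogenicity tables (9.6, mITT) can mix study-vaccine and approved-vaccine responses; the protocol lists no pre-vaccine summary and specifies no recording of the vaccination date after Day 43

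*Combined protocol and SAP*

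**What the plan says.** **Analysis set.** Section 9.6: "The mITT Population will be used for all listings and summary statistics corresponding to immunogenicity analysis". Section 9.2 defines mITT as Safety Population subjects with any serology data and sets no cut-off at receipt of another vaccine. The endpoints in 3.2.2 (GMT, GMT ratio as placebo over TAP-COVID-19, GMFR, GMI, seroconversion) run to Day 365. For the rest, 9.6 defers: "Additional details for analysis of immunogenicity are presented in the SAP".

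**What is barred.** Exclusion criterion 24 covers "Receipt of any other approved SARS-CoV-2 vaccine prior to the first study vaccine or within 90 days after administration of the first study vaccine". Criteria 25 and 26 bar experimental coronavirus vaccines and investigational vaccines through the end of the study. Section 6.7.1 separately asks subjects not to have vaccinations while they participate unless the investigator prescribes them.

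**Expected recipients.** Under 9.2, subjects given an approved vaccine "will be captured as a subset analysis of the PP Population at Days 90, 181, 273, and 365", and this is "based on the date of receiving an approved COVID-19 vaccine". Section 9 gives an illustrative list of subsets that includes "subjects that received an FDA Emergency Use Authorization/licensed COVID vaccine".

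**Data capture.** Section 4.1: "AEs and concomitant medications will be captured through Day 43", and then "SAEs, MAAEs, NOCDs, and AESIs only will be captured after Day 43 to study completion". Section 6.7.1 and Table 1-1 note n set the same Day 43 limit on medications. Note j describes telephone visits as asking about exposure to the virus. Medical history is updated at later clinic visits, and 11.1.1 requires known protocol deviations to be recorded. None of these mentions vaccine product or date.

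**The concern.** An approved spike-based vaccine would be expected to raise RBD and neutralising titres in either arm. Once subjects may receive one, an all-samples GMT or GMT ratio at a late visit no longer shows how long the TAP-COVID-19 response persists relative to placebo. A placebo subject vaccinated elsewhere can also count as seroconverted, because seroconversion in 3.2.2 rests on detectable anti-RBD antibody.

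The subset that the protocol names describes the recipients. A reader interested in persistence needs the opposite: samples taken before the approved vaccine. Both summaries depend on the same variable, the date of that vaccine, and the protocol does not say that anyone records it after Day 43.

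**Working it through.** The plan states no figure on this point, so there is none to reproduce. The check has four steps.

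**1. Visits that fall outside the bar (Table 1-1 windows, criterion 24).** Dose 1 is Day 1, so 90 days later is Day 91.

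| Visit | Window (days) | Against Day 91 |
|---|---|---|
| Day 43 and earlier | up to 45 | inside the bar |
| Day 90 | 76–104 (29 days) | Days 92–104 (13 days) fall after it |
| Day 181 | 167–195 | wholly after |
| Day 273 | 259–287 | wholly after |
| Day 365 | 351–379 | wholly after |

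**2. Days without specified medication capture.** 365 − 43 = 322 days (Days 44–365). Of these, 91 − 43 = 48 days (Days 44–91) fall while criterion 24 still applies.

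**3. Effect on the GMT ratio.** Uptake and titres are not in the documents, so this step is illustration. Let G be the TAP GMT without an approved vaccine, R·G the placebo GMT, and K·G the GMT of recipients in both arms. Uptake is uP (placebo) and uT (TAP). Assume that recipients are otherwise like non-recipients. Because the log GMT is a mean of logs:

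log(reported ratio) = (1 − uP)·log R + (uP − uT)·log K

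With equal uptake u, the term in K vanishes and the reported ratio is R^(1−u):

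| True R (placebo/TAP) | u = 20% | u = 40% | u = 60% |
|---|---|---|---|
| 0.05 | 0.09 | 0.17 | 0.30 |
| 0.10 | 0.16 | 0.25 | 0.40 |
| 0.25 | 0.33 | 0.44 | 0.57 |

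For example, 0.10^0.8 = 0.158 and 0.10^0.4 = 0.398. With unequal uptake and K above 1, the second term pushes the ratio up if uP exceeds uT and down if uT exceeds uP. The net movement can therefore go either way.

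For seroconversion, 9.3 plans 30 placebo subjects per part. At 20%, 40% or 60% uptake, up to 30u = 6, 12 or 18 of them could be counted because of the approved vaccine.

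**4. Precision of a summary restricted to pre-vaccine samples.** Start from the planned 30 per arm per part; the number actually enrolled is not in the documents, and the Amendment 8 rationale says enrolment had ended. At 20%, 40% or 60% uptake, 24, 18 or 12 per arm remain. The log10 SD is assumed to be 0.5 (range 0.4–0.6). The 95% CI factor on the GMT ratio is 10^(t × SD × √(1/n1 + 1/n2)), with t the 0.975 quantile on n1 + n2 − 2 degrees of freedom.

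| n per arm | SD 0.4 | SD 0.5 | SD 0.6 |
|---|---|---|---|
| 30 | 1.61 | 1.81 | 2.04 |
| 24 | 1.71 | 1.95 | 2.23 |
| 18 | 1.87 | 2.18 | 2.55 |
| 12 | 2.18 | 2.65 | 3.22 |

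**The case against.** The other side has real points.

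- **The SAP was not available.** Section 9 places all analyses in a separate SAP, 9.6 defers to it, and the Section 9 subset list is given only as examples. A missing pre-vaccine summary in the protocol does not show that none is planned. This stands, and it makes the analysis part of the point conditional.
- **Recipients are already separated.** Section 9.2 does so at Days 90, 181, 273 and 365, and non-recipients are the complement. This stands in part. The complement is not listed as a summary, it would drop a later recipient's earlier samples, and it still needs the vaccination date.
- **Not specified is not the same as not collected.** The eCRF is not among the documents. History updates occur at the same four visits as the 9.2 subset, and deviation records may pick up known cases. A reader might infer that the date is missing or that the subset cannot be built; the documents do not support that. They show only that the protocol does not say the date is recorded.
- **Experimental vaccines are barred throughout.** A reader might take the 90-day limit to cover every non-study COVID-19 vaccine. Criteria 25 and 26 rule that out; the limit applies to approved vaccines.
- **A lost or reversed difference is speculation.** The formula allows it if uptake differs widely between arms. Subjects, investigators and site staff stay blinded to study completion (6.6.2), and a subject whose code is released early is withdrawn (6.6.3.1). The documents give no basis for the size of any imbalance.

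Section 6.7.1 does not remove the problem, because 9 and 9.2 plan for recipients despite it.

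**Conclusion.** The point holds in this form. Following the stated rules, all-samples immunogenicity summaries at Days 181, 273 and 365, and in up to 13 of the 29 days of the Day 90 window, can combine responses to the study vaccine and to an approved vaccine. The visible protocol offers a recipient subset but no pre-vaccine summary, and it leaves unstated how the date that defines the subset is obtained after Day 43.

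The size cannot be fixed from the documents. The figures in step 3 of the working rest on assumed uptake, equal uptake in both arms and equal post-vaccine titres. They show that the distortion could matter for reading persistence; they do not predict it.

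The affected endpoints are secondary and descriptive, with no formal testing. A reader should not extend the point to the primary reactogenicity endpoint or to the Day 43 review, since both lie inside the barred period. This is a cheap improvement. Confidence is medium, because the SAP and eCRF could already answer part of it.

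**What to change.** 1. **Record the date.** In 6.7.1 and Table 1-1 note n, state that product and date of any non-study COVID-19 vaccine are recorded at the existing visits and telephone contacts through Day 365, retrospectively where contacts have passed, unless the eCRF already does so. Cost: one dated item at seven existing contacts (Days 76, 90, 120, 150, 181, 273, 365), part of it by recall because enrolment had ended by this version.
2. **Add a pre-vaccine summary.** In 9.6 or the SAP, keep the all-samples mITT table at Days 90, 181, 273 and 365. Beside it, add a by-treatment summary restricted to samples taken before any non-study COVID-19 vaccine. Label it as smaller and self-selected, note that it still includes responses to natural infection, and base statements on persistence of the TAP-COVID-19 response on it. A cross-reference suffices if the SAP already has it. Cost: one paragraph and one set of late-visit tables, with fewer subjects and the wider intervals shown in step 4 of the working.
3. **Align the text.** Sections 9.2 (PP) and 9.6 (mITT) should name the same population for the recipient and pre-vaccine summaries, or say why they differ. Criterion 24 and the 6.7.1 instruction on vaccinations must be reconciled; which rule applies is for the sponsor to settle.
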